## Quantification of Tumor and Organ at Risk (OAR) Volume and Motion Path Changes during Definitive Photon or Proton Beam Radiotherapy

### PROTOCOL OVERVIEW

In recent years, conformal techniques have been developed that allow for precise delivery of radiotherapy to the primary tumor and regional lymphatics while minimizing the dose to normal tissues. These approaches are predicated upon precise anatomic localization of the regions to be irradiated. Unfortunately, at present, most conformal treatment delivery approaches do not account for changes in tumor volume, tumor motion or changes in patient anatomy during the time course of definitive radiotherapy. Proton beam radiotherapy can potentially allow for ultra-precise delivery of treatment due to the physical characteristics of the proton beam. Therapeutic proton beam radiotherapy allows for the elimination of exit dose and a significant reduction in the entrance dose to the patient while maximizing dose delivered to the tumor (Figure 1). However, accurate treatment delivery with proton beam radiation is predicated upon precise definition of tumor volume and location. Tumor volume reduction during definitive proton beam radiotherapy has resulted in significant dosing errors, with dose deposition in unintended regions (MDACC PTCOG 47). The purpose of this protocol is to quantify the extent of tumor volume, motion, and anatomic changes that occur during the tumor course of definitive photon beam radiotherapy. As both proton beam and photon beam radiotherapy have nearly identical biological efficacy, the changes observed during photon beam radiotherapy should closely approximate that which would likely be observed during proton beam irradiation.

**Quantification of Tumor and Organ at Risk (OAR) Volume and Motion Path Changes during Definitive Photon or Proton Beam Radiotherapy**

Figure 1: Comparison of Dose Deposition between Photon and Proton Beam Radiotherapy

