**Primary Aim**

To estimate the degree of tumor volume, tumor motion and patient anatomy change during treatment with photon beam radiotherapy using 4D or 3D CT Scans and/or a serial of MR Imaging.

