## **1.0 ABSTRACT**

In recent years, conformal techniques have been developed that allow for precise delivery of radiotherapy to the primary tumor and regional lymphatics while minimizing the dose to normal tissues. Unfortunately, at present, most conformal treatment delivery approaches do not account for changes in tumor volume, tumor motion or changes in patient anatomy during the time course of treatment. Studies have shown that lung, head and neck, and gynecological tumors can change significantly during radiation treatment. Patients can lose significant weight during the radiation treatment, which can alter the patient's body habitus and anatomy. These tumor and anatomical changes can alter radiation dose distribution, resulting in higher radiation doses to normal tissue and lower radiation doses to target volumes. Adapting for changes in tumor motion, tumor volume and patient anatomy can therefore enhance radiation treatment efficacy and widen the therapeutic ratio. Because proton beams require precise target definition, accounting for tumor changes should be critical when using proton beam radiation treatment.

This is a pilot study to quantify the tumor and organ at risk volume and motion path changes that occur during definitive proton beam or photon beam radiotherapy. The patients will undergo CT scans in treatment planning position at the time of CT Simulation. Photon beam treatment plans and proton beam treatment plans will be generated from these images. Based on the location of the primary tumor, patients will undergo either up to weekly 3D or 4D CT and/or a serial of MR scans during treatment. These images will be compared to the initial CT and/or MR scans used for treatment planning and analyzed for changes in tumor volume and tumor anatomic location. At the end of treatment, the /serial images will be compared to the initial treatment planning images to quantify the changes in tumor volume and tumor motion during the course of radiation treatment. Each CT and/or MR scan will also be used to evaluate the changes in dose distribution to the target volumes and normal tissues that occur with the initial photon treatment plan and initial proton treatment plan. The changes in tumor volume, tumor motion and dose distribution during the course of radiation treatment will be analyzed to determine the effect of tumor changes on radiation treatment efficacy.

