### 3.0 SPECIFIC AIMS/OBJECTIVES

**Specific Aim 1:** To estimate the degree of tumor volume, tumor motion and patient anatomy change during treatment with photon beam radiotherapy.

- 1a. To estimate the degree and impact of tumor volume change during the course of definitive photon radiotherapy treatment in lung cancers, head and neck cancers, gastrointestinal cancers (including but not limited to colorectal and rectal cancers) and gynecological cancers.
- 1b. To estimate the degree and impact of tumor motion (anatomic location) change during the course of definitive photon radiotherapy treatment in lung cancers, head and neck cancers, gastrointestinal cancers (including but not limited to colorectal and rectal cancers and gynecological cancers).
- 1c. To estimate the degree and impact of changes in patient anatomy during the course of definitive photon radiotherapy treatment in head and neck and upper gastrointestinal cancers.

Hypothesis: Tumor volume and motion will change over the course of radiation treatment in patients with lung cancers, head and neck cancers, gastrointestinal cancers (including but not limited to colorectal and rectal cancers) and gynecological cancers. The weight loss experienced by patients with upper gastrointestinal and head and neck cancers will have a significant impact on their anatomy. These changes will alter the dose distribution of the photon beam treatment plans, possibly limiting radiation dose delivery to the target volumes and increasing radiation toxicity to surrounding critical structures.

**Specific Aim 2:** To estimate the error if tumor volume, tumor motion and patient anatomy change during treatment with proton beam radiotherapy.

- 2a. To generate simulated proton beam plans using serial CT or MR imaging obtained from either photon or proton beam patients to estimate the dosimetric error if these changes are unaccounted for during proton treatment.

[figure not shown]
Hypothesis: The changes in tumor volume and motion and patient anatomy will have a greater effect on appropriate dose distribution in plans using proton beam therapy compared to photon beam therapy given the need for more accurate target delineation in proton beam therapy.

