### **6.6. *On Treatments***

Based on the primary tumor location and the discretion of the treating radiation oncologist, patients will undergo 3D/4D CT Scan (up to weekly) and/or MR Scan (minimum of 3).. The GTV, ITV and critical normal structures will be contoured on each up to weekly/serial scan. The up to weekly/serial GTV volume will be compared to the initial GTV volume to determine changes in tumor volume. Each GTV will be compared to the initial ITV volume to determine what percent of the GTV resides within the initial ITV. This value will be used to evaluate changes in tumor motion. Each ITV will be compared to the initial ITV. The initial photon treatment plan and proton treatment plan will be applied to the new scan. The amount of radiation dose to each GTV, ITV and critical normal structures will be recorded to determine the changes in dose distribution that occur as treatment progresses. **SUBJECTS WILL RECEIVE ALL SCANS IN THE RADIATION ONCOLOGY CLINIC OF THE UNIVERSITY OF PENNSYLVANIA.**

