### **9.3 *Objectives:* To determine changes over time in:**

1. tumor volume variables
2. tumor motion
3. patient anatomy
4. dose distribution to tumor and critical normal organs

**9.4 Endpoints:** To be measured at baseline and then weekly during 7-8 weeks of radiotherapy

1. GTV (gross tumor volume), the volume of the primary tumor visualized on the CT scan
2. ITV (interior tumor volume), the GTV expanded to include interior motion (i.e., breathing or swallowing) such that the tumor resides within the ITV during normal motion
3. CTV (clinical tumor volume), the ITV expanded to include microscopic disease (margins)
4. PTV (planning tumor volume), the CTV expanded by several mm, as determined by radiation dosimetry planning, PTV is considered the ultimate target volume

NOTE the relationship: GTV < ITV < CTV < PTV

5. Dose coverage: at each scan time point, determine the percent of the GTV which resides within the baseline ITV or CTV
5. patient weight and percent weight loss from baseline
6. Radiation dose to critical normal organs based on dose-volume histograms (i.e., 20 Gy to 50% of normal lung tissue)

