**9.5 Plans for Data Analysis: To be conducted within each stratum**

1. Tumor Volume: To determine the distributions of volume variables and percent change from baseline. At each scan time point, compute mean, median, range and standard deviation of these variables and plot mean values over time. To compare volume variables at baseline to the values at selected scan time points by paired Wilcoxon signed ranks test.
2. Tumor Motion: At each scan time point, compute mean, median, range and standard deviation of the dose coverage and plot mean values over time. To compare ITV or CTV variables at baseline to the GTV at selected scan time points by paired Wilcoxon signed ranks test.
3. Patient Anatomy: To determine the distribution of patient percent weight loss. At each scan time point, compute mean, median, range and standard deviation of percent weight loss and plot mean values over time.
4. Dose distribution: To determine the distributions of radiation dose to GTV, ITV and critical normal organs. To correlate radiation dose to normal organs with percent weight loss.
5. Conduct exploratory longitudinal analyses to examine changes over time in the 30 patients. Random effects linear regression models will be employed to estimate changes in variables over time clustered by patient. Natural log transformation will be applied prior to modeling.
6. To assess if changes in volume variables are clinically relevant and if so, identify the earliest time point at which re-calibration is warranted. Although it may not be possible to identify a single 're-calibration solution' for all patients in a particular stratum, we will attempt to identify the earliest scan time point at which the majority of patients have clinically important changes in tumor volume or location resulting in over-shoot of the target volume and/or increased dose exposure to normal organs.

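### Section 9 has no organ-at-risk volume or position endpoint, so the organ changes named in the title and Abstract would be reflected only indirectly, through organ dose

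*Combined protocol and SAP*

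**What the plan says.** The title is "Quantification of Tumor and Organ at Risk (OAR) Volume and Motion Path Changes during Definitive Photon or Proton Beam Radiotherapy". The Abstract (Section 1.0) gives the purpose of the pilot as to "quantify the tumor and organ at risk volume and motion path changes". Section 9.1 counts the tumor's proximity to critical organs among the quantities that are fixed from the pre-treatment CT and assumed not to change appreciably. Section 9.2 says the serial scans are there to measure changes in patient anatomy as well as in the tumor.

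The formal aims are worded more narrowly. The Primary Aim is "To estimate the degree of tumor volume, tumor motion and patient anatomy change during treatment with photon beam radiotherapy using 4D or 3D CT Scans"; serial MR may be used as well or instead. Aim 1c in Section 3.0 begins "To estimate the degree and impact of changes in patient anatomy during the course of definitive photon radiotherapy treatment in head and neck and upper", the last site being upper GI tumors.

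On data, Section 6.6 states: "The GTV, ITV and critical normal structures will be contoured on each up to weekly/serial scan". The same section compares the GTV and ITV with baseline for volume and position. For normal structures it records dose only, with the initial photon and proton plans applied to each new scan.

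On analysis, the one anatomy endpoint in Section 9.4 is "patient weight and percent weight loss from baseline", and the one organ endpoint is dose from dose-volume histograms. Section 9.5 item 3 is "Patient Anatomy: To determine the distribution of patient percent weight loss". Item 4 describes organ dose and correlates it with percent weight loss.

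**The concern.** The title and Abstract promise organ volume and motion results, and the organs are outlined on every scan, but Section 9 never turns those outlines into a volume or position variable. Body weight does not come from a scan, so the statement in 9.2 that imaging measures anatomy has no matching endpoint.

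Three things are at stake. First, a team following Section 9 exactly would have no direct result on how organs at risk change in size or position. Second, when organ dose changes under the initial plan, the only explanatory variable planned is weight loss. The analysis could not separate an organ that shrank from one that moved, or from one that received dose because the tumor shrank. Third, the study is meant to inform whether and when to re-plan, and organ geometry added after the data are seen would be an unplanned analysis.

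**Working it through.** **Plan's own figure.** Section 9.2 gives 30 patients per stratum in four strata: 4 × 30 = 120, which agrees with the total under Required Sample Size. There is no power calculation to reproduce, because 9.2 calls the study descriptive.

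**Tracing each part of the stated purpose to Section 9.**

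| Stated purpose | Endpoint in 9.4 | Analysis in 9.5 |
|---|---|---|
| Tumor volume | GTV, ITV, CTV, PTV (4) | Item 1 |
| Tumor motion | Percent of GTV inside baseline ITV or CTV (1) | Item 2 |
| Patient anatomy | Weight and percent weight loss (1) | Item 3 |
| Dose to normal organs | Dose-volume histogram measures (1) | Item 4 |
| Organ volume | None | None |
| Organ position or motion path | None | None |

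The count is 4 + 1 + 1 + 1 = 7 endpoints (the numbering in 9.4 uses 5 twice). None of the seven is an organ volume, displacement or overlap.

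Of the six items in 9.5, items 4 and 6 mention normal organs, in both cases by dose. Item 5 models the study variables over time but adds none, and no organ geometry variable is on the list it draws from.

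**How many scans are involved.** Section 9.4 has weekly measurement over 7 to 8 weeks of treatment.

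- Weekly scanning in every patient: 120 × 7 = 840 and 120 × 8 = 960 on-treatment scans. This is a maximum, because CT is only up to weekly.
- Three scans per patient (the MR minimum in 6.6 and 9.2): 120 × 3 = 360.
- Patients within Aim 1c: head and neck (30) plus the upper part of the GI stratum (at most 30), so at most 60. At the weekly maximum that is 60 × 7 = 420 to 60 × 8 = 480 scans.

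**What the added endpoints could deliver.** The 95% confidence interval half-width for a stratum mean, in SD units, is t(0.975, n − 1)/√n.

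- n = 30: 0.37 SD.
- n = 27: 0.40 SD.
- n = 24: 0.42 SD.

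The values 27 and 24 are assumed losses; the documents give neither a dropout rate nor an SD for any organ measure. Precision of this order suits a descriptive pilot, so N need not change.

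**The case against.** The strongest reply is that organ geometry is already used. Under 6.6 the initial plan is held fixed and recalculated on each scan with the organs re-contoured, so a change in organ dose partly reflects a change in organ size or position. That stands. It means the contours are not wasted, and it addresses the impact part of Aim 1c. A reader might infer that Aim 1c rests on body weight alone, or that the scans yield nothing on organs; the documents support neither. What dose cannot do is report the geometric change itself, and Section 9.3 lists patient anatomy and dose distribution as separate objectives.

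A second reply is that organ volume and motion appear only in the title and one sentence of the Abstract. The Overall, Primary, Secondary and Specific Aims and the objectives in 9.3 speak of patient anatomy. This also stands, and it is why narrowing the title and Abstract is a legitimate alternative for whatever is not measured. It does not settle the matter, because 9.2 says the scans measure anatomy.

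A third reply is that weight follows the protocol's own rationale: Sections 1.0 and 2.0 describe anatomy change as a result of weight loss, and Aim 1c is confined to the sites where weight loss is expected. That makes weight a reasoned variable to keep. But the hypothesis under Aim 1 treats weight loss as the cause and anatomy as what is affected, so weight alone leaves the affected quantity unmeasured. Section 9.5 also applies item 3 in every stratum, whereas the weight-loss rationale in Section 2.0 covers head and neck and gastrointestinal cancers only. The NSCLC and gynecologic strata make up 60 of the 120 patients.

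**Conclusion.** The point holds as a mismatch between stated purpose and endpoints. Organ-at-risk volume and position are not directly measured in 9.4 or 9.5; they are reflected only through organ dose under the fixed initial plan, although the contours needed to measure them are already planned. The tumor and dose results are unaffected, so this is a change that should be made rather than one on which the study depends.

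The scans concerned number 840 to 960 at the very most, and 360 if each patient has three. The conclusion rests on the text and not on these counts. It would be tempting to state what share of anatomy change weight captures, but the documents give no correlation between weight and organ displacement, so no such figure is offered.

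**What to change.** **Section 9.4.** Add, from the contours already drawn under 6.6 and for critical organs named in advance per stratum:

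- organ volume and its percent change from baseline;
- organ displacement, or percent overlap with the organ's baseline contour, after alignment to the planning scan. State the alignment method, since serial CT and MR may both be used and the documents describe none.

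**Section 9.5.** In item 3, summarise these at each scan time point with the statistics already listed there. In item 4, relate organ dose change to them as well as to percent weight loss. Keep weight as a supporting variable.

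**Title and Abstract.** Displacement between scans is not a motion path, and Sections 4.0 and 6.5 leave 4D imaging to the treating radiation oncologist. Either restrict any organ motion path claim to patients with 4D imaging, or narrow the title and Abstract for what is not measured.

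**Cost.** Wording changes, some extra analysis and image alignment work. No additional patients or scans are needed. A change in the external body contour is left out of this list because 6.6 does not include that contour among the structures drawn; measuring it would be additional work.

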### ***9.6 Sample Size/Study Duration***

Patient heterogeneity (e.g., size and location of the tumor, radiation dose/fractions, proximity to critical normal organs, tumor shrinkage and dramatic weight loss) are all key factors in this evaluation. As such, we seek to enroll a sufficiently large series of diverse patients in each stratum. This pilot study will enroll 30 patients per stratum in approximately 1 year (e.g., NSCLC) up to 4 years (e.g., gynecologic cancers), depending on the particular stratum. Once a stratum has enrolled the target number, the study remains open but enrollment to that particular stratum is closed. We expect that the entire study will take approximately 5 years to complete.

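### Section 9.5 item 4 correlates normal-organ dose, not change in that dose, with percent weight loss, although the stated objective is change in dose

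*Combined protocol and SAP*

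**What the plan says.** The statistical section (9.3) lists what the study is to determine changes over time in; its fourth entry is "dose distribution to tumor and critical normal organs". Section 6.6 explains how organ dose is obtained: "The initial photon treatment plan and proton treatment plan will be applied to the new scan", and dose is recorded "to determine the changes in dose distribution that occur as treatment progresses". Each organ therefore has a photon and a proton value at every scan on which dose is recalculated.

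The endpoints in 9.4 include "patient weight and percent weight loss from baseline" and "Radiation dose to critical normal organs based on dose-volume histograms". Percent weight loss is defined against baseline; organ dose is not.

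Item 4 of 9.5 asks for the distributions of dose and then: "To correlate radiation dose to normal organs with percent weight loss". It names no change from baseline, scan or plan type. Item 1 of the same list, on tumor volume, does name the change: "To determine the distributions of volume variables and percent change from baseline". All analyses in 9.5 are to be run within stratum, with 30 patients in each.

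**The concern.** The dose in an organ at a later scan is the planned dose plus whatever has changed since. Weight loss during treatment can plausibly affect only the second part. A correlation using the level also carries the first part, which was fixed before any weight was lost.

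That first part will vary, because 9.6 seeks diverse patients within each stratum. The factors it names include "radiation dose/fractions, proximity to critical normal organs, tumor shrinkage and dramatic weight loss". The GI stratum runs from esophageal to anal tumors (5.1), and the Aim 1 hypothesis places weight loss in upper GI and head and neck cancers. Within the GI stratum, tumor site could therefore influence both planned organ dose and weight loss, and a level correlation could reflect site and not anatomical change.

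At stake is the impact part of Aim 1c, which concerns photon treatment in head and neck and upper GI cancers. Item 4 is the only listed analysis that relates weight loss to organ dose. Item 5 models unspecified variables over time, and item 6 looks for increased organ dose; neither brings in weight loss.

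**Working it through.** **The plan's own figure.** None is attached to this correlation. The only relevant number is 30 patients per stratum; 4 × 30 = 120 agrees with the stated total. The documents give no standard deviation, correlation or effect size for organ dose, so the rest is illustration.

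**Level against change.** Write later dose as D = B + C, where B is baseline (planned) dose and C is the change. Let r be the correlation of C with weight loss, r_b the correlation of B with weight loss, and k = SD(B)/SD(C). If B and C are uncorrelated,

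r_level = (r + k·r_b) / √(1 + k²).

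Take r = 0.60 (assumed). With r_b = 0, the level correlation is 0.60/√(1 + k²). It equals the change correlation when r_b = r(√(1 + k²) − 1)/k, and it is zero when r_b = −r/k.

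| k (assumed) | 1/√(1 + k²) | r_level at r_b = 0 | r_b at which level = change | r_b at which level = 0 |
|---|---|---|---|---|
| 0.5 | 0.89 | 0.54 | 0.14 | not reachable |
| 1 | 0.71 | 0.42 | 0.25 | −0.60 |
| 2 | 0.45 | 0.27 | 0.37 | −0.30 |

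Below the break-even r_b the level correlation understates the change correlation; above it, it overstates it. The error can go either way.

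**Precision at n = 30.** The 95% interval is tanh(atanh(r) ± 1.96/√27):
- r = 0.60: 0.31 to 0.79
- r = 0.42: 0.07 to 0.68
- r = 0.27: −0.10 to 0.57

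**Is replacing level by change enough?** Not if scans are analyzed together without a time term. Weight loss and tumor shrinkage both accumulate during treatment, and 9.1 and 9.6 name both as relevant. This was simulated with 30 patients, 5 scans, both processes growing linearly and independent between patients, and a random-intercept model of dose change on same-scan weight loss. Shrinkage was given half of, or the same effect as, a unit weight-loss slope.
- True weight-loss slope 0: the model without time gives about 0.35 or 0.71.
- True slope 1: it gives about 1.35 or 1.71.
- With scan time added, the slopes return to 0 and 1.

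A second set of runs gave 0.33 to 0.67 and 1.34 to 1.67 without time, and again 0 and 1 with it.

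**The case against.** The strongest reply is that the documents already show what is meant. Section 9.3 puts dose under changes over time, 6.6 records dose for that purpose, and the Methods overview speaks of variations in dose distribution. On this view item 4 is merely terse. Much of this stands: change is the likely intent, and a reader who inferred that the investigators had deliberately chosen a level would go beyond the text. But item 1 states change where change is meant, item 4 does not, and an analyst following item 4 could correlate planned dose, last-scan dose or all scans pooled. Those are different quantities.

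It can also be said that the plan type and scan are partly supplied. Aim 1c is about photon treatment, and percent weight loss is zero for everyone at baseline, so only later scans are informative. That is fair, and it narrows the gap. It still leaves two plans per scan and several scans per patient without a rule.

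A reader might use the 40–80 Gy prescription range in 6.5 to put a value on k. The documents do not support this. That range depends on the site of the primary tumor, whereas the analysis is within stratum, and prescriptions are limited by normal-tissue constraints, so organ dose need not be proportional to prescription.

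Nor does the re-calibration question in item 6 depend on this correlation; it rests on clinically important changes and increased organ dose.

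**Conclusion.** The point holds as a mismatch between the variable written in item 4 and the objective it serves. Followed literally, the correlation combines planned-dose differences between patients with dose change and can mis-estimate the weight-loss impact in Aim 1c. The reach is limited to that aim: photon treatment, head and neck and upper GI. The size and direction cannot be known from the documents. The figures above depend on assumed values of r, r_b and k, and on planned dose and dose change being uncorrelated.

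A reader might infer that the correlation will necessarily be diluted, or that a hypothesis test would fail. Neither follows: the direction depends on r_b, and 9.2 calls the study descriptive and not powered for testing. The estimate is nonetheless the product of a descriptive study, and the repair costs little. It should be fixed.

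**What to change.** Reword item 4 as follows in substance:
- For each patient, organ and post-baseline scan, compute the change in the named dose-volume metric from the baseline value of the same initial plan. Use the initial plans throughout, as 6.6 does, even for a patient who is re-planned.
- Pair that change with percent weight loss at the same scan.
- Within stratum, fit a model with a patient random effect and a term for scan time. Add change in GTV as a further covariate or as a sensitivity analysis. Leave the change untransformed, because the log in item 5 cannot be applied to zero or negative values.
- Report the photon plan as the Aim 1c analysis and the proton plan separately.

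The cost is SAP wording, modest extra analysis and a less precise weight-loss slope once time is included. The analysis is restricted to scans with both a recalculated dose and a recorded weight. Weight is listed among the weekly endpoints in 9.4 but has no weekly row in the 6.4 calendar, so a weight field at each scan on the case report form would help. Section 6.6 does not say how dose is recalculated on MR, and scans where it cannot be recalculated would drop out. No change to treatment or sample size is involved.
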